- if at least 3 fasting SMBG diary measurements from the past 7 days exceed 220 mg/dl (12.2 mmol/l). Diary fasting SMBG values that meet these criteria should be recorded in the eCRF.

The last HbA1c and FPG values measured by central laboratory prior to the up-titration of insulin dose will be carried forward for the efficacy analyses at week 24 (visit 9).

Reduction of daily insulin dose shall be ordered by the investigator under the following circumstances:

Within the first 7 days of active randomized treatment:

- if the patient reports two or more readings of plasma glucose value ≤ 80 mg/dl (≤ 4.4 mmol/l).

After the first 7 days of active randomized treatment:

- if the patient reports two or more readings of plasma glucose value ≤ 70 mg/dl (≤ 3.8 mmol/l).

Patients should be encouraged to contact the investigator in such a case to allow the reduction of insulin dose.

Background OAD therapy may only be decreased if a concern of hypoglycaemia arises in a patient that has already been completely taken off of insulin.

Background OAD therapy may not be increased at any time during the study

Patients will be discontinued from the study if they have had complete withdrawal of both insulin and if applicable other OAD, they subsequently experience more than one event of major hypoglycaemia, and the investigator decides that current treatment puts the patient at risk of either repeated hypoglycaemic events or major hypoglycaemia. Major hypoglycaemia is defined as a symptomatic event requiring external assistance due to severe impairment in consciousness or behaviour with a capillary or plasma glucose value < 3 mmol/l (< 54 mg/dl) and prompt recovery after glucose or glucagon administration.

Randomized patients who discontinue early should complete the procedures described for visit 18 (end of treatment period) immediately following discontinuation of study drug. Thereafter patients should return for the 3 week follow up visit so that visit 19 procedures can be completed.

Long-term, double-blind extension period I (Visits 10–12, Weeks 25-48)

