3.3.2 Inclusion criteria

For inclusion in the study subjects must fulfil all of the following criteria:

Inclusion criteria at enrolment (visit 1):

1. Provision of a written informed consent
2. Men and women diagnosed with type 2 diabetes
3. Age ≥ 18 - ≤ 80 years at time of consenting
4. Patients with inadequate glycaemic control, defined as HbA1c $\geq 7.5\%$ and $\leq 10.5\%$, and who, according to investigators judgement, are on a stable insulin regimen, with a mean dose of at least 30 IU of injectable insulin per day, for a period of at least 8 weeks prior to enrolment. Patients may also be treated with maximally two OADs under the approved prescribing information. OAD treatment should be at a stable dose for a period of at least 8 weeks.

Patients on metformin therapy should be on at least 1500 mg/day of metformin or at the maximum tolerable dose for a period of at least 8 weeks prior to enrolment. Patients on other OAD medications should be on at least half maximum daily recommended dose of the OAD for a period of at least 8 weeks prior to enrolment.

Inclusion criteria before randomisation (visit 2):

1. Patients with HbA1c $\geq 7.5\%$ and $\leq 10.5\%$ according central laboratory values measured from sample taken at visit 1 and who are on a stable insulin regimen with a mean insulin dose of least 30 IU of injectable insulin per day either without any other OADs or with a stable dose of OADs that have been approved in combination with insulin.
2. Daily insulin requirements over the past seven days with insulin dose documentation that does not vary more than 10% on more than one occasion of the calculated mean daily insulin dose at visit two (For example for patient whose calculated mean daily insulin dose at visit 2 is 50 IU, daily doses in the preceding seven days with insulin dose documentation may not be <45 and >55 IU on more than one occasion).

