3.3.3 Exclusion criteria

Any of the following is regarded as a criterion for exclusion from the study:

Exclusion criteria at randomization visit (visit 2):

1. Clinical diagnosis of type 1 diabetes, MODY or secondary diabetes mellitus (eg chronic pancreatitis, partial pancreatectomy).
2. Symptoms of poorly controlled diabetes that in judgement of the investigator would preclude participation in this trial including, but not limited to, marked polyuria and polydipsia with greater than 10% weight loss during the 3 months prior to enrolment.
3. Treatment with more than two additional OADs
4. History of diabetes insipidus

5. Use of inhaled insulin or injectable GLP-1 receptor agonists or DPP-4 inhibitors within 8 weeks of enrolment visit
6. Calculated Creatinine Clearance <50 ml/min/1.73m² (calculated by Cockcroft-Gault formula) or a measured serum creatinine value of >2 mg/dl (177 μ mol/l). Patients on concomitant metformin therapy will be excluded if serum creatinine ≥ 1.5 mg/dl (133 μ mol/l) for male subjects and ≥ 1.4 mg/dl (124 μ mol/l) for female subjects
7. Known condition of congenital renal glucosuria
8. Total bilirubin >34.2 μ mol/l, >2.0 mg/dl
9. Creatine kinase ≥ 3 xULN
10. Hemoglobin ≤ 10.0 g/dl (≤ 100 g/l) for men; hemoglobin ≤ 9.5 g/dl (≤ 95 g/l) for women
11. Thyroid-stimulating hormone (TSH) values outside normal range confirmed by abnormal T4 values
12. Positive serologic evidence of current infectious liver disease including patients being positive for Hepatitis B viral antibody IgM, Hepatitis B surface antigen and Hepatitis C virus antibody.
13. Any clinically significant abnormality identified on physical examination, ECG or laboratory tests, which in the judgement of the investigator would compromise the patients' safety or successful participation in the clinical study.
14. Significant cardiovascular history within the past 6 months prior to the screening visit, defined as: myocardial infarction, unstable angina pectoris, transient ischemic attack, unstable or previously undiagnosed arrhythmia, cardiac surgery or revascularization (coronary angioplasty or bypass grafts), or cerebrovascular accident
15. Pregnant or breastfeeding patients
16. Treatment with glucocorticoids equivalent to oral prednisolone >10 mg (betametasone >1.2 mg/dexametasone >1.5 mg/hydrocortisone >40 mg)/day within 30 days prior to enrolment; topical or inhaled corticosteroids are allowed
17. History of bariatric surgery

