- (d) Confirmed increase in serum creatinine of ≥ 0.5 mg/dl (44 $\mu\text{mol/L}$) for patients with baseline creatinine of < 1.4 mg/dl (123 $\mu\text{mol/L}$) or confirmed increase in serum creatinine of ≥ 1 mg/dl (88 $\mu\text{mol/L}$) for patients with baseline creatinine of ≥ 1.4 mg/dl (123 $\mu\text{mol/L}$). Patients with serum creatinine above these values will have their study medication held and a repeated serum creatinine test within 7 days. If serum creatinine is still elevated as specified above (≥ 0.5 mg/dl or ≥ 1.0 mg/dl above baseline), the patient should discontinue the clinical study medication. Otherwise study medication may be resumed unless otherwise contraindicated. For further details please see [Appendix G](#) of this protocol.
- (e) CK >10 x ULN confirmed at a repeated measurement within 24 hours.
- (f) Patients with a central laboratory ALT and/or AST >3 x ULN will be scheduled for a follow-up visit within 3 calendar days following the receipt of the result. See [Appendix H](#) for further guidance.
- Patients should be discontinued from study if the initial and repeat laboratory tests meet any of the following criteria:
- ALT and/or AST are >3 x ULN and TB >1.5 x ULN
 - ALT and/or AST are >5 x ULN for ≥ 14 consecutive days, at any time after initial confirmatory results
 - ALT and/or AST are >8 x ULN
- (g) No longer applicable
- (h) Serum sodium ≤ 125 mmol/l with or without symptoms: dosing of blinded study medication will be interrupted. For further detail please follow instructions stated in [Appendix E](#).
- (i) Haemoglobin ≤ 9.0 g/dl (90 g/l).

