3.4.3 Insulin and other background OAD treatment

Patients will be instructed not to take any insulin or OAD medication on the morning of the study visit. In the morning prior to each visit, acceptable concomitant medications can be taken with water only. For further information on insulin- and background OAD treatment please refer to section 3.1.

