3.7 Pre-study, concomitant and post-study treatment(s)

3.7.1 General medication

Other medication than described in Exclusion Criteria section 3.3.3 and Discontinuation Criteria section 3.3.5.1 which is considered necessary for the patient's safety and well-being (e.g., to treat illnesses or complaints that occur during the study), may be given at the discretion of the Investigator(s). The administration of all medication (including investigational product and placebo and other medication in use within 30 days prior to the day of enrolment and during the course of the study) must be recorded in the appropriate sections of the Electronic case report form (eCRF). The specific type of medication (trade or generic name), the indication for use, and the dates of usage should be reported. The calculated total daily dose of injectable insulin and used other OAD should also be recorded.

In principle any changes in concomitant medication should be avoided unless medically indicated. If concomitant medication has to be changed - including but not limited to diuretics, antihypertensive drugs and lipid lowering therapy - this must be recorded in the appropriate sections of the eCRF.

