1. CASE IDENTIFICATION AND MANAGEMENT OF DECREASED RENAL FUNCTION

The evaluation of renal function is an important part of the overall safety assessment in the dapagliflozin clinical development program. In order to standardize the definition and management of decreased renal function, the following guidelines has been developed:

- a) **For patients with baseline creatinine of <1.4 mg/dl (123 µmol/L), an absolute increase in serum creatinine level of ≥ 0.5 mg/dl (44 µmol/L) from baseline based on central laboratory results**

- b) **For patients with baseline creatinine of ≥ 1.4 mg/dl (123 µmol/L), an absolute increase in serum creatinine level of ≥ 1.0 mg/dl (88 µmol/L) from baseline based on central laboratory results**

In either of these circumstances, the investigator should consider evaluating the patient for potentially reversible causes of renal dysfunction including but not limited to:

1. concurrent use of NSAIDS, antibiotics, or other medications known to affect measures of serum creatinine
2. volume depletion
3. urinary tract infection
4. obstructive uropathy

Patients should return for repeat central laboratory testing as soon as possible, no later than 7 days after the abnormal result. Study drug should be interrupted pending the results of repeat testing. If after interruption the serum creatinine value remains above the increase limit described above (³0.5 mg/dl or ³1.0 mg/dl above baseline), the patient should permanently discontinue the medication and be withdrawn from the study (in which case an Adverse Event must be reported).

If after study drug interruption the serum creatinine value has decreased to below the increase limit (<0.5 mg/dl or <1.0 mg/dl above baseline), study drug can be re-started if appropriate in the investigator's judgment and after consultation with the study delivery team physician. If study drug is re-started, the patient should return for a follow-up central lab serum creatinine 7-14 days after re-start, although more frequent assessments may be done at investigator discretion. If the patient restarts study drug and the serum creatinine value increases again to the increase limit (³0.5 mg/dl or ³1.0 mg/dl above baseline), the patient should permanently discontinue the medication and be withdrawn from the study (in which case an Adverse Event must be reported).

Clinical Study Protocol Appendix H

Drug Substance	Dapagliflozin
Study Code	D1690C00006
Edition Number	3
Date	

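### The only permitted reason to reduce a background OAD is hypoglycaemia after insulin has been stopped; read literally, any other safety or label reason leaves an unchanged dose or withdrawal

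*Protocol*

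**What the plan says.** Section 3.1 gives the rule for the 24-week period and repeats it for extension periods I and II; section 4.7.4.1 repeats it again: "Background OAD therapy may only be decreased if a concern of hypoglycaemia arises in a patient that has already been completely taken off of insulin". The synopsis agrees in substance: patients stay on their prior OAD dose for the whole study, and the only changes it names concern insulin.

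Section 3.4.3 is the section on insulin and background OADs, and it points to one place: "For further information on insulin- and background OAD treatment please refer to section 3.1".

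Section 3.7.1 deals with medication in general. It mentions OADs in a recording instruction ("The calculated total daily dose of injectable insulin and used other OAD should also be recorded") and then says: "In principle any changes in concomitant medication should be avoided unless medically indicated". It neither excludes OADs nor refers to 3.1.

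Three other provisions bear on metformin:

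- Inclusion criterion 4 (section 3.3.2): "Patients may also be treated with maximally two OADs under the approved prescribing information". This is an entry condition.
- Exclusion criterion 6 (section 3.3.3): "Patients on concomitant metformin therapy will be excluded if serum creatinine" is at or above 1.5 mg/dl in men or 1.4 mg/dl in women. This is checked at randomisation.
- The on-study renal rule (section 3.3.5.1, item 7(d)) acts on a rise of at least 0.5 mg/dl from a baseline below 1.4, or at least 1.0 mg/dl from a baseline of 1.4 or more: "Patients with serum creatinine above these values will have their study medication held and a repeated serum creatinine test within 7 days". If the rise is confirmed, Appendix G says "the patient should permanently discontinue the medication and be withdrawn from the study". Neither text gives an instruction about metformin.

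After an OAD reduction, the last earlier HbA1c and FPG values are carried forward. This is stated for week 24 (section 4.7.4.1) and week 104 (section 3.1, extension II). It is not stated for week 48, and section 6.4.1 provides for censoring only at insulin up-titration.

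**The concern.** The OAD sentence is a closed rule: it names one permitted reason and excludes the rest. A patient may need a lower OAD dose for a reason other than hypoglycaemia, such as an adverse effect, a label restriction or declining renal function on metformin. Metformin users enter on at least 1500 mg/day or their maximum tolerable dose, and the study drug carries volume depletion and renal impairment as potential risks in Appendix I.

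A site that follows 3.1 can keep the dose or withdraw the patient. A site that relies on the general wording in 3.7.1 can lower the dose, but risks a protocol deviation. The patient's safety is at stake, and so is retention in a study of up to 104 weeks for safety, body weight and insulin dose. Sites may also act differently in the same situation.

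**Working it through.** **Step 1: the texts side by side.**

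| Question | Text | Answer for a non-hypoglycaemic reason |
|---|---|---|
| May an OAD be reduced? | 3.1 (three periods), 4.7.4.1 | No |
| Which section governs OADs? | 3.4.3 | 3.1 |
| May concomitant medication change? | 3.7.1 | Yes if medically indicated; OADs neither excluded nor clearly included |
| Does the label permit an on-study change? | 3.3.2 | Entry condition only |
| What does the renal rule act on? | 3.3.5.1 7(d), Appendix G | Study drug and participation; silent on metformin |
| What other safety route exists? | 3.3.5.1, reasons 2 and 5 | Discontinue the patient |

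Because 3.4.3 sends the reader to 3.1, the specific rule is the more natural one to follow. What remains under it is an unchanged dose or withdrawal.

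**Step 2: how far renal function can fall before the renal rule acts.** Let B be baseline creatinine (mg/dl) and T the level at which the rule acts: T = B + 0.5 if B < 1.4, and T = B + 1.0 if B ≥ 1.4. With age and weight held fixed, Cockcroft-Gault clearance varies as 1/creatinine, so the fall at T is 1 − B/T.

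| B | T | Fall in clearance at T |
|---|---|---|
| 1.0 | 1.5 | 1 − 1.0/1.5 = 33.3% |
| 1.2 | 1.7 | 1 − 1.2/1.7 = 29.4% |
| 1.39 | 1.89 | 1 − 1.39/1.89 = 26.5% |
| 1.40 | 2.40 | 1 − 1.40/2.40 = 41.7% |
| 1.49 | 2.49 | 1 − 1.49/2.49 = 40.2% |

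**Step 3: the trigger against the metformin entry limit.** The limit is used only as a yardstick from the protocol. It is not an on-study action level.

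- Men, T − 1.5: B = 1.1 gives 0.1; 1.3 gives 0.3; 1.39 gives 0.39; 1.40 gives 0.90; 1.49 gives 0.99.
- Women, T − 1.4: B = 1.0 gives 0.1; 1.2 gives 0.3; 1.39 gives 0.49.
- There is no interval for men with B ≤ 1.0 or women with B ≤ 0.9.

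So a metformin user can pass the creatinine at which the protocol would have refused entry without meeting the renal trigger. The 0.90 to 0.99 figures apply only to men with a baseline of 1.40 to 1.49. The position can also persist after a trigger. Appendix G lets study drug restart once the rise is below the limit, so a man with baseline 1.3 could restart at 1.79 (a rise of 0.49) with no metformin instruction.

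**Step 4: scheduled creatinine.** From the study plan and Table 6, samples fall at weeks 0, 1, 4, 8, 12, 16, 20, 24, 32, 40, 48, 52, 65, 78, 91 and 104. The gaps are 4 weeks from week 4 to 24, 8 weeks from week 24 to 48, 4 weeks from 48 to 52, and 13 weeks thereafter.

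These figures show how far apart the rules lie. They do not show how many patients are affected.

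**The case against.** **Context.** In section 3.1 the sentence sits among the rules for lowering insulin at low glucose. It can be read as setting an order of glycaemic down-titration, insulin first and OAD last. Two of the four places go on to say what happens if an OAD has to be reduced. This narrower reading is reasonable, and a site may adopt it. The wording is still exclusive, and the reductions it foresees are those it has just permitted.

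**3.1 against 3.7.1.** A reader might infer a direct contradiction. The documents do not support that. Section 3.4.3 points to 3.1, and the examples in 3.7.1 are diuretics, antihypertensives and lipid-lowering drugs, although that list is open. The fair statement is that 3.7.1 does not clearly override 3.1. If 3.1 prevails, the prohibition stands.

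**Metformin threshold.** A reader might infer that the protocol keeps patients on metformin past a level at which it must be stopped. The documents do not support that either. The 1.5 and 1.4 mg/dl limits apply at entry, and any on-study stopping level would have to come from a label that is not in the documents.

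**Existing protection.** It would be wrong to say that nothing happens below the renal trigger. Section 4.7.2.1 returns results within 72 hours, flags values outside the normal range and asks the investigator to assess them. Section 4.7.1.2 makes clinically significant deterioration an adverse event, and reasons 2 and 5 in 3.3.5.1 allow discontinuation. Nothing forbids an unscheduled test. A confirmed trigger ends participation, and treatment in follow-up is unrestricted. All of this stands. It protects the patient by ending participation and does not permit the dose change.

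**Primary result.** A withdrawn patient is handled by LOCF, and one with an OAD reduction has the last earlier HbA1c carried forward. The week-24 value is much the same either way. This also stands.

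**Conclusion.** The point holds as a defect in a conduct rule. Read literally, sections 3.1 and 4.7.4.1 bar an OAD reduction for any safety or label reason other than hypoglycaemia off insulin, and leave an unchanged dose or withdrawal. It is a stated prohibition, so it is not a detail left to the SAP.

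Its practical size is modest. The renal illustration is confined to metformin users with a baseline above 1.0 mg/dl (men) or 0.9 mg/dl (women). It assumes fixed age and weight, and it uses the entry limit only as a yardstick. The protocol gives neither the share on metformin nor the number affected. The number is probably small, since Appendix I reports no change in mean or median creatinine at week 12 of the Phase IIb study. The gain from correcting the rule is patient safety and retention for safety, weight and insulin-dose data. The effect on the primary result is small, and the sample size is unaffected. The change should be made; confidence is medium because a narrower reading of the sentence is available.

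**What to change.** 1. In section 3.1 (24-week period, extension I, extension II) and section 4.7.4.1, extend the OAD sentence: *or if a reduction or interruption is required for patient safety or by the OAD's approved prescribing information (for example metformin with a confirmed decline in renal function)*. State that this does not require withdrawal from the study.
2. In section 3.7.1, say that background OADs follow section 3.1.
3. State the HbA1c and FPG carry-forward after any OAD reduction for week 48 (section 3.1, extension I) and in section 6.4.1, so that it matches the existing rules for weeks 24 and 104.
4. Fix no creatinine value here. If the sponsor's physicians choose one, it should need a confirmatory repeat, as the renal rule does: a man with baseline 1.4 would reach 1.5 on a single reading 0.1 higher.

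The cost is one amendment: a clause in four places, one cross-reference and two carry-forward statements. No scheduled visits are added, since creatinine is already measured at every clinic visit; an affected patient may need one repeat test. The downside is that later HbA1c and FPG values are replaced by carried-forward values in those patients, and background therapy becomes slightly less fixed.

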This is a 24-week, international, randomized, parallel-group, double-blind, placebo-controlled Phase III study with a 24-week double-blind extension period I and a 56-week double-blind-extension period II incorporating a switch of dapagliflozin 5 mg to 10 mg during extension period II to evaluate the efficacy and safety of dapagliflozin as add-on therapy in adult patients with type 2 diabetes who have inadequate glycaemic control ($HbA1c \geq 7.5\%$ and $\leq 10.5\%$) on ≥ 30 IU injectable insulin daily for at least 8 weeks prior to enrolment, with or without OADs.

Target subject population

Male and female patients with type 2 diabetes and age ≥ 18 to ≤ 80 years, with inadequate glycaemic control defined as $HbA1c \geq 7.5\%$ and $\leq 10.5\%$ are eligible to enter the Enrolment period. Patients must be according to investigators judgement on a stable insulin regimen with the mean insulin dose of ≥ 30 IU injectable insulin for at least 8 weeks prior to enrolment. Additional treatment with OADs according to their approved prescribing information is allowed. Patients will be stratified according to whether their treatment regimen includes OADs or not. No more than 60% of the enrolled patients can be taking insulin plus OADs. Enrolment in the strata with OADs may be stopped to ensure adequate numbers of patients who are not taking any OADs. OADs must be at a stable dose for at least 8 weeks prior to the enrolment visit. Patients on metformin therapy should be on at least 1500 mg/day of metformin or at the maximum tolerable dose for a period of at least 8 weeks prior to enrolment. Patients on other OAD medications should be on at least half maximum daily recommended dose of the OAD for a period of at least 8 weeks prior to enrolment. Patients on more than 2 background OADs may not be included in the study.

Target subject population for the long-term, double blind extension period II

Patients who are still on active study treatment after the first 48 weeks of double-blind treatment, have not developed any criterion for study discontinuation and are willing to participate in the second extension period for another 56 weeks.

Investigational product, dosage and mode of administration

- Dapagliflozin tablets, 2.5 mg, 5 mg and 10 mg, administered orally, once daily for the 24-week double-blind treatment period and the 24-week long term double-blind extension period I .

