3.3.5 Discontinuation of subjects from treatment or assessment

3.3.5.1 Criteria for discontinuation

The study may be terminated at individual centres if the study procedures are not being performed according to GCP or if recruitment is slow. AstraZeneca may also terminate the entire study prematurely if concerns for safety arise within this study or in any other study with dapagliflozin.

Patients may be discontinued from study treatment and assessments at any time. Specific reasons for discontinuing a patient are:

1. Voluntary discontinuation by the patient who is at any time free to discontinue his/her participation in the study, without prejudice to further treatment
2. Safety reasons as judged by the investigator, AstraZeneca and/or Bristol-Myers Squibb Pharmacovigilance
3. Severe non-compliance to protocol as judged by the investigator and/or AstraZeneca
4. Incorrect enrolment i.e., the patient does not meet the required inclusion/exclusion criteria for the study
5. Any clinical adverse event, laboratory abnormality or intercurrent illness which, in the opinion of the investigator, indicates that continued participation in the study is not in the best interest of the subject.
6. Patient lost to follow-up (as defined by the inability to reach the patient after 3 documented phone calls, fax, email, or attempts to contact him/her through patient locator agencies (if allowed per national regulation) and having sent one letter by registered/certified mail; all should be documented in the patient's medical records).
7. Development of study specific discontinuation criteria listed below. These criteria include one or more of the following parameters:
 - (a) Treatment with glucocorticoids equivalent to oral prednisolone >10 mg/day (two temporary periods of higher daily doses but no longer than 7 days each are allowed)
 - (b) Severe hypoglycaemic events, defined as ≥ 1 major hypoglycemia in spite of complete withdrawal of insulin and if applicable other OAD and the investigator decides that current treatment poses the patient at risk of either repeated hypoglycemic events or major hypoglycaemia.
 - (c) Pregnancy identified by positive pregnancy test or otherwise verified

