3.7.2 Prohibited and restricted medication and herbal/over-the-counter therapy

For prohibited and restricted medication, see Exclusion Criteria section 3.3.3 and Discontinuation Criteria section 3.3.5.1.

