9.4 Procedures in case of pregnancy

If a patient becomes pregnant, the investigational product should be stopped and the AstraZeneca representative should be informed. The pregnancy report module in the eCRF should be completed by the investigator and the AstraZeneca representative will forward the information to BMS using the same procedure as for SAE reporting. The outcome of each pregnancy will also be collected once this information is available.

Pregnancy itself is not regarded as an AE unless there is a suspicion that the investigational product under study may have interfered with the effectiveness of a contraceptive medication. However, the outcome of all pregnancies (spontaneous miscarriage, elective termination, normal birth or congenital abnormality) must be followed up and documented even if the patient was discontinued from the study.

All reports of congenital abnormalities/birth defects are SAEs. Spontaneous miscarriages should also be reported and handled as SAEs. Elective abortions without complications should not be handled as AEs. All pregnancies must be reported on the pregnancy module in the eCRF. All outcomes of pregnancy must be reported to AstraZeneca on the pregnancy outcomes report that will be available in the Investigator Study File

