1. ALGORITHM ON MANAGEMENT OF SUSTAINED ELEVATED LIVER SAFETY ABNORMALITIES

The monitoring for liver safety will be performed using the serum levels of AST, ALT and TB (see Figure 1 algorithm flow chart).

Patients with central laboratory ALT and/or AST >3 ULN will be scheduled for a follow-up visit within 3 days following receipt of the initial laboratory results, to obtain repeat central laboratory ALT, AST, TB and Alkaline Phosphatase (ALK-P). In the event that the repeat laboratory assessments cannot be obtained within 3 days, the Investigator is encouraged to discuss possible alternatives with the Sponsor. Patients should remain on study medication until confirmatory results are obtained, unless otherwise contraindicated.

- **If the repeat ALT and AST are ≤ 3 ULN**, subject should continue in the double-blind treatment according to their original visit schedule unless otherwise contraindicated.
- **If the repeat ALT and/or AST are >3 ULN but ≤ 8 ULN and TB ≤ 1.5 ULN**, the subject's medical history, including details of risk factors for liver diseases should be evaluated for potential underlying etiologies. In addition, specialized blood sampling will be performed to evaluate liver function as well as identify potential causes of laboratory elevation(s). The Investigator should continue to monitor the subject's liver tests every 3 days following receipt of the prior laboratory results until the ALT and AST are ≤ 2 ULN or until ALT and AST are at or below baseline levels. The frequency of retesting can decrease to once a week or less if abnormalities stabilize and the subject is asymptomatic. Patients should remain on study medication unless confirmatory results indicate that a criterion for discontinuation has been met or continuing study medication would be otherwise contraindicated.

Patients must be discontinued from the study if an initial and repeat confirmatory laboratory tests meet any of the following criteria:

- **ALT and/or AST are >3 ULN and TB >1.5 ULN**
- **ALT and/or AST are >5 ULN for ≥ 14 consecutive days, at any time after initial confirmatory results**
- **ALT and/or AST are >8 ULN**

Note: See below for discontinuation procedures.

Guidance on Assessment of Hepatic Laboratory Abnormalities

The following is presented to assist in the evaluation and management of hepatic laboratory values. It is not intended to supplant Investigators' clinical judgment.

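### The stopping rule for major hypoglycaemia after all insulin and OADs are withdrawn is set at two events in section 3.1 and at one event in the formal criteria

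*Protocol*

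**What the plan says.** The rule concerns a patient whose insulin, and any background OAD, has been completely withdrawn and who then has major hypoglycaemia. The protocol states it in five places.

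- **Section 3.1** gives it once for the 24-week double-blind period, once for extension period I and once for extension period II. Each time the patient is to be discontinued if "they subsequently experience more than one event of major hypoglycaemia" and the investigator decides that current treatment puts the patient at risk.
- **Section 3.3.5.1, item 7(b)**, the formal list of discontinuation criteria, has: "Severe hypoglycaemic events, defined as ≥ 1 major hypoglycemia in spite of complete withdrawal of insulin". The OAD condition and the investigator's judgement of risk follow, as in section 3.1.
- **Section 3.3.3, item 4(b)**, in the exclusion list applied at visit 12 before extension period II, uses the same wording as item 7(b).

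Section 3.3.5.1 opens with "Patients may be discontinued from study treatment and assessments at any time" and then lists the specific reasons, of which item 7 is one.

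**The concern.** Population, type of event and investigator judgement are the same in all five places, and only the event count differs. A site that looks up the rule in section 3.1 may conclude after a first major event that the criterion is not yet met. A site that looks it up in section 3.3.5.1 will conclude that it is. Section 3.4.3 sends readers to section 3.1 for insulin and OAD handling, so the first route is a natural one.

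The matter at stake is safety handling. A major event, as section 3.1 defines it, needs help from another person because of severe impairment, with glucose below 54 mg/dl. In these patients the background glucose-lowering drugs have already been stopped, so none is left to reduce. Appendix I, section 1.2.2, accepts that combining dapagliflozin with other antidiabetic agents might increase hypoglycaemia, and it counts the protocol's discontinuation guidelines among the safeguards. That safeguard should give one answer wherever it is read.

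**Working it through.** The protocol gives no figure to reproduce, so the check is a comparison of texts.

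**Thresholds side by side**

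| Place | Events needed | Investigator judgement also needed |
|---|---|---|
| Section 3.1, 24-week period | 2 or more | Yes |
| Section 3.1, extension I | 2 or more | Yes |
| Section 3.1, extension II | 2 or more | Yes |
| Section 3.3.5.1, item 7(b) | 1 or more | Yes |
| Section 3.3.3, item 4(b) | 1 or more | Yes |

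The three statements in section 3.1 repeat one rule and item 4(b) repeats item 7(b), so this is one discrepancy and not several.

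**Outcome by event count**, for a patient off all insulin and OAD whom the investigator judges to be at risk

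| Major events | Section 3.1 | Items 7(b) and 4(b) |
|---|---|---|
| 0 | Not met | Not met |
| 1 | Not met | Met |
| 2 or more | Met | Met |

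The versions disagree only in the middle row.

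**Visit 12.** Entry to extension period II is consistent with the lower threshold. The synopsis admits patients who "have not developed any criterion for study discontinuation"; section 3.1 and note j of Table 1 say the same in substance, and item 4(b) excludes on one event. A patient with one event during extension I, judged at risk, need not be withdrawn under section 3.1 but is barred from extension II for that same event. The conflict is therefore mainly about handling during treatment.

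**Possible number of patients.** The document gives no rate for this event. The Phase 2b study in Appendix I had no confirmed hypoglycaemic event, but it lasted 12 weeks and cannot supply a rate for a 104-week trial. As an assumption, let 0% to 0.5% of the 808 randomised patients (section 6.5) have exactly one such event:

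- lower end: 808 × 0 = 0
- upper end: 808 × 0.005 = 4.04, about 4 patients

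**The case against.** The best defence is that the texts can be read as two steps: withdrawal is permitted after one event, because section 3.3.5.1 opens with a permissive verb, and required after two, because section 3.1 is directive. Neither sentence is then broken. But the opening verb covers the whole list, including items that are plainly not optional. For the liver criteria, item 7(f) says "Patients should be discontinued from study if the initial and repeat laboratory tests meet any of the following criteria" and Appendix H says "Patients must be discontinued from the study if an initial and repeat confirmatory laboratory tests meet any of the following criteria". For pregnancy, section 9.4 says "If a patient becomes pregnant, the investigational product should be stopped". It is fair to reply that those items are made firm by their own text and that item 7(b) has no such wording, so this point weakens the two-step reading without excluding it. What counts more is that no two-step rule is stated anywhere, that item 7 presents its entries as the study-specific discontinuation criteria, and that item 4(b) excludes on a single event.

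Three further points stand and limit the finding:

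- Items 2 and 5 of section 3.3.5.1 let the investigator withdraw any patient on safety grounds at any event count. Section 4.7.4.1 also asks patients to contact the investigator after a major event. Few decisions should change.
- The group is very narrow. Patients enter on at least 30 IU of insulin a day with HbA1c of at least 7.5%, must come off insulin and any OAD completely, and must then have a major event.
- The 0.5% upper bound has no source in the document. It illustrates scale and is not evidence of frequency.

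It can also be said that the protocol does not rank the two sections, so the intended threshold is unknown. That is true, but section 3.7.2 tells readers to "see Exclusion Criteria section 3.3.3 and Discontinuation Criteria section 3.3.5.1", and section 3.7.1 uses the same label. This is a reasonable ground for treating section 3.3.5.1 as the reference.

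**Conclusion.** The inconsistency is real. One operative safety threshold is stated in two ways in the current text and is not reconciled anywhere. Its severity is minor. It matters only for a patient with exactly one major event after complete withdrawal of insulin and any OAD, whom the investigator judges to be at risk. Under the stated assumption that is 0 to about 4 patients, and it may be none. There is no material effect on the analysis sets, type I error, power or the HbA1c result. The conclusion about the wording rests on the text alone; only the patient count depends on an assumption.

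**What to change.** In each of the three statements in section 3.1, replace the count with one or more events of major hypoglycaemia and add a cross-reference to section 3.3.5.1, item 7(b). Keep the investigator-judgement condition, and notify sites. This brings section 3.1 into line with items 7(b) and 4(b) and adopts the more protective threshold. If the sponsor in fact intended two events, items 7(b) and 4(b) should be changed instead; what is needed is a single threshold throughout.

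The cost is the same edit in three places and a memo to sites. The downside is possibly a few more withdrawals. Analysis sets, alpha, power and sample size stay as they are.
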